#### 8. INTERVENTION DISCONTINUATION

For the purposes of this trial, the intervention is either of two technical variants of surgical decompression for CM+SM, PFD or PFDD. While it is possible that intra-operative factors that could influence a surgeon's plan to carry out the intended procedure (PFD or PFDD), this would be highly unlikely. Nevertheless, if the surgical technique is aborted or changed during the

procedure, participants will be followed per study protocol with all associated clinical care and data collection.

# 9. STATISTICAL CONSIDERATIONS

# 9.1 General Design Issues

The Central Hypothesis of this proposal is that, compared with PFDD, PFD will result in fewer surgical complications and thus less harm to patients within 12 (+/- 2 months) months of surgery. With a more favorable risk profile and non-inferior effect on clinical outcome and syrinx size compared with PFDD, PFD will be associated with superior QOL. In the case where the patient returned outside planned study follow-up window, a secondary analysis will include those visits up to 24 months.

This study is designed as a cluster randomized controlled trial (C-RCT) of the two major neurosurgical treatments for CM+SM: posterior fossa decompression with duraplasty (PFDD) and extradural posterior fossa decompression (PFD). This design was chosen with input from site investigators (neurosurgeons) in order to obtain participation from a large number of pediatric neurosurgeons and reduce crossovers and non-participation resulting from physician bias. While there is inherent individual surgeon bias, clinical equipoise exists across the field; this is underscored by the participation of >50% of the pediatric neurosurgeons in the United States in this RCT and support of this study by the AANS, the CNS, and the Joint AANS/CNS Pediatric Section.

**Specific Aim 1:** Determine if PFD is associated with fewer surgical complications and less harm to patients than PFDD.

**Hypothesis:** PFD will be associated with fewer surgical complications and less potential harm to patients than PFDD.

Anticipated Outcome: Cerebrospinal fluid (CSF)-related complications  $\leq 6$  months (e.g. CSF leak, pseudomeningocele, aseptic meningitis, infection, and hydrocephalus) and requirement for additional surgery for wound revision or CSF diversion will be lower after PFD compared with PFDD.

**Specific Aim 2**: Determine if PFD provides non-inferior clinical improvement and syrinx regression compared to PFDD.

**Hypothesis:** Clinical improvement and syrinx regression provided by PFD will be non-inferior compared to those provided by PFDD.

Anticipated Outcome: Clinical symptoms, neurological function, and syrinx regression  $\leq 12$  months will be non-inferior following PFD when compared with PFDD. Rates of revision decompression surgery (PFD or PFDD) and progression of spinal deformity  $\leq 12$  months after PFD also will be non-inferior to PFDD.

**Specific Aim 3**: Determine if PFD is associated with superior QOL compared to PFDD. **Hypothesis:** With fewer surgical complications, PFD will be associated with superior QOL compared with PFDD.

Anticipated Outcome: PFD will have superior QOL and will show improvements in overall QOL over time ( $\leq 12$  months post-operatively) compared to PFDD. In particular, both physical

metrics (evaluated by pain frequency, pain severity and non-pain symptoms) and psychosocial metrics will improve at a higher rate and in a shorter period of time after PFD compared to PFDD.

#### 9.2 Sample Size and Randomization

#### 9.2.1 Treatment Assignment Procedures

This study is designed as a cluster randomized controlled trial (C-RCT) of the two major neurosurgical treatments for CM+SM: posterior fossa decompression with duraplasty (PFDD) and extradural posterior fossa decompression (PFD). This design was chosen with input from site investigators (neurosurgeons) in order to obtain participation from a large number of pediatric neurosurgeons and reduce crossovers and non-participation resulting from physician bias. During extensive discussions with PRSRC investigators and patient partners, there was significant concern for selection bias due to crossovers and selective enrollment if individual patients were randomized, a known problem in surgical trials [33]. Site investigators felt that having their entire practice randomized to one technique would increase surgeon comfort and experience with that approach, thereby decreasing tendencies for biased enrollment. Consequently, individual PRSRC centers will be randomized to perform either PFDD or PFD. In this design, PRSRC centers will be serve as the unit of inference for comparing PFDD and PFD, and the cluster size is expected to be 6 per center. For cluster randomization, a computer-generated randomization sequence will be generated independently by the study statistician. Overall sample size of up to 238 participants will be enrolled. Approximately 50% participants per procedure over the enrollment period.

Potential participants will be identified, screened, and recruited through the clinical practices of 36 participating PRSRC sties in addition to 8 other sites. In this trial, the randomization unit will be the PRSRC center; therefore, the same intervention will be used for all qualifying patients enrolled at each center. If a surgeon in a PRSRC center strongly believes that a patient should undergo a certain procedure (PFDD or PFD), the patient will not be randomized. Effective randomization will occur through the random distribution of patients to centers employing each procedure (PFDD and PFD).

# 9.3 Interim analyses and Stopping Rules

The Posterior Fossa Decompression with or without Duraplasty for Chiari type I Malformation with Syringomyelia study will appoint an independent Data Safety Monitoring Board (DSMB) of members. The DSMB will meet once prior to the start of the study, and will approve the final protocol prior to its implementation. Additionally, the DSMB will establish a charter to guide its function. The charter would include rules of procedure, definitions of a meeting quorum, and information about meeting logistics.

The purpose of the DSMB is to advise PCORI, the Principal Investigator ([name]), and the Investigators Committee regarding the continuing safety of study participants and the continuing validity and scientific merit of the study. The DSMB is responsible for monitoring accrual of study subjects, adherence to the study protocol, assessment of data quality, performance of individual clinical sites, review of serious adverse events and other subject safety issues, and review of formal interim statistical analyses of treatment efficacy. The DCC

will send reports relating to these topics to DSMB members 10 days prior to each DSMB meeting. Based on prospectively defined guidelines to be outlined in the DSMB charter, the DSMB should recommend whether or not to terminate enrollment in the *Posterior Fossa Decompression with or without Duraplasty for Chiari type I Malformation with Syringomyelia* study because of potential safety concerns or high evidence of efficacy. The DSMB will also have the option to recommend stopping the study due to low likelihood of finding an effect if the trial continues (futility), or if the risks/benefit ratio is not favorable. Each DSMB meeting will result in a summary report that will be provided to the Investigator Committee, PCORI, and each local IRB.

#### 9.4 Outcomes

The goal of this study is to supply patients and families with the information about the risks and benefits of PFDD and PFD that *they feel* are most important in making informed clinical decisions. As such, the primary outcome of interest is reduction in harm to patients, measured as surgical complications and/or requirement for reoperation for complication management  $\leq 12$  (+/- 2 months) months after initial PFDD or PFD. Complications and reoperation are associated with additional pain as well as emotional and psychological stress, longer hospital stays, and lost time from school/work. Secondary outcomes focus on efficacy outcomes and will include: 1) comparison of pre-operative symptoms and neurological deficits at  $\leq 6$  weeks, 3-6 months, and 12 (+/- 2 months) months after surgery and syrinx size and spinal alignment (coronal and sagittal Cobb angles) at 12 (+/- 2 months) months after surgery; and 2) assessment of QOL (including psychosocial and physical dimensions) at baseline,  $\leq 6$  weeks, 3- 6 months, and 12 (+/- 2 months) months after surgery. This outcome will be evaluated using the CHIP and the HUI-3 QOL instruments.

Because this is a surgical trial, an Adjudication Committee, consisting of two pediatric neurosurgeons and one pediatric neuroradiologist and independent of the design and conduct of the trial, will adjudicate the primary outcome measure. The committee will review the primary endpoint based on a blinded review of clinical notes, data forms and imaging studies. Decisions by the adjudication committee will determine final outcomes. Consensus definitions of CSF-related complications following neurosurgery have been developed [34]. These definitions have been reviewed and approved by the neurosurgeons participating in the study, and will be used in this trial. Likewise, the extent of syrinx resolution following surgery will be determined by centralized review of blinded imaging studies. By contrast, treatment failure (i.e. need for revision PFDD or PFD) will be determined individually by the treating surgeon in consultation with the patient/family, since such decisions are inherently subjective and based both on the surgeon's level of concern and the patient's discomfort and relative acceptance to the inherent risks of surgery (either PFD or PFDD).

#### 9.5 Data Analyses

# *A Priori* Plans for Data Analysis Descriptive Statistics

Using CONSORT guidelines for cluster-randomized trials,53 We will present descriptive statistics, for continuous variables the mean (+/-standard deviation) or median (minimum, maximum) values

and for categorical variables the frequencies and proportion for each cluster; These presentations will be carried out at baseline and at 12-month follow-up. We will provide reasons for dropouts.

#### **Final Comparative Analysis**

*Planned sensitivity analyses to determine the impact of key assumptions:* Due to the fact that each patient in a given center will be assigned to the same procedure, it is possible to observe unequal overall sample sizes for each procedure. The initial analysis plan is to give equal weights to all clusters. If there is imbalance in the prognostic factors, we will use weighted analyses where the cluster-level summary score is weighted inversely proportional to the reciprocal of its estimated variance.

#### Comparison methods

The primary outcome is a binomial outcome measured as a surgical complication and/or requirement for reoperation for complication management  $\leq 6$  months after initial PFDD or PFD. To account for within cluster correlation, possibly variable cluster size and the relatively small number of clusters in this cluster randomized trial, generalized estimating equations (GEE) with small-sample correction or random effect logistic regression will be used for the primary analysis of this cluster randomized trial [35, 36].

Secondary outcomes include Treatment Efficacy variables and Quality of Life variables. Continuous variables measured at 3 time points over the 12 (+/- 2 months) month follow-up will be analyzed using longitudinal analysis with linear mixed models including the random cluster effect. Binomial and ordinal data will be analyzed using GEE methods accounting for cluster. In the case where the patient returned outside the planned study follow-up window, a secondary analysis will include those visits up to 24 months.

Missing data: Based on PRSRC data and early data from this trial, loss to follow-up rate is expected to be low (<2%). To prevent missing data, we will meet with patients at 1 month, 3-6 months and at 12+/-2 months after the procedure. Every effort, including phone call reminders to patients, will be made to decrease loss to follow-up. Loss to follow-up, missing data, and the reasons leading to loss of follow-up or data will be recorded. In case of missing data, we will impute missing data using different methods. Because of the repeated measures nature of the data, the 'last observation carried forward' method will be utilized [37]. In addition, Buck's method, which is the extended version of regression imputation, will be used [38]. The Buck's imputation will be based on the observed values of patient's age, CM ( $\geq$  5mm tonsillar ectopia), syrinx diameter, and pre-operative comorbidities. In addition to the overall rates of missing data for each procedure, because of the cluster randomized trial, we will also monitor the missing data within each cluster and center and report the discrepancy between the loss to follow-up rates for each procedure. Special attention will be given and separately reported if the entire cluster is loss to follow-up. As a sensitivity analysis for the missing data, study results will be compared for the following three conditions: 1) patients with missing primary outcome variable are excluded from analyses; 2) results with last observation carried forward, and 3) results with Buck's method. Robustness of the results under each scenario will be assessed

Heterogeneity of Treatment Effect (HTE): As an exploratory analyses, to assess if the procedure is most beneficial for a specific subgroup, the heterogeneity of the effect of performing PFDD vs PFD will be assessed within the following pre-determined subgroups based on: 1) patient age at the time of surgery (<5 years, 5-12 years, 13-18 years); 2) CM status (5-12 mm tonsillar ectopia, >12 mm tonsillar ectopia) [39]; 3) syrinx diameter (3-6 mm, 7-9 mm); and 4) preoperative hydrocephalus or neuromuscular disease, two comorbidities associated with increased morbidity following pediatric CM +/- SM surgery [40]. Demographic and comorbidity data will be collected by trained study research assistants/coordinators with strict oversight by site investigators using standard data collection forms. As the 5th subgroup, the effect of surgeon's experience on the occurrence of surgical complications and requirements for re-operations for complications for each procedure during the 1st vs 2nd year of the award period will be assessed. For HTE analysis, the test of procedure (PFD vs PFDD) by subgroup effect (such as age) interaction will be performed to assess the homogeneity of the procedure effect within each subgroup. If the test of interaction indicates a significant interaction for any subgroup, then, Gail and Simon's test of qualitative interaction will be performed [41]. All pre-specified subgroup analyses (patient's age, CM status, syrinx diameter, comorbidity, and surgeons' experience) will be reported regardless of observing a statistically significant or not-significant effect.

Sub-analysis by Syrinx size (3-6 mm, 7-9 mm): A planned subgroup analysis for the syrinx diameter will be performed. Each of the three specific aims will be separately analyzed within the syrinx diameters of 3 to 6 mm and 7 to 9 mm for exploratory purposes. The test of interaction will be used to assess if the treatment effect is homogeneous within each of the syrinx size subgroups (3-6 mm vs 7-9 mm). If the test of interaction indicates heterogeneity, using the whole 3 to 9 mm syrinx diameter range, analyses will be performed, to identify, if any, a cut-off point to propose using one surgical method over the other. For example, whether the PFD is associated with greatly fewer surgical complications when the syrinx diameter is less than 5mm, but surgical complication rates are similar for PFD and PFDD when the syrinx diameter is >6 mm will be examined.

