Based on the enrolled 47 patients in the database with complete data as of 11/28/17, the average cluster size is 2.9. If we assume each center enrolls 3 more patients over the enrollment extension, the average cluster size increases to 5.9. With the current ICC estimate of <0.01 and using the original estimates for the complication rates (17.8% in PFDD and 2.7% in PFD), with the projected sample size of 145, we can still reach 84% power by enrolling patients from 24 centers with an average cluster size of 6. The same power level can also be achieved by enrolling patients from 30 centers with an average cluster size of 5.

It should be noted that it is assumed that the average cluster size is 6 in all centers for these calculations. The design effect (DE) concept is used in cluster randomized trials to inflate the sample size of the study, compared to the traditional randomized trials [44]. When cluster size is fixed,  $DE = 1 + (m - 1) \times ICC$ ; where m is the average cluster size and ICC is the intraclass correlation coefficient. In other words, the sample size of the study can be calculated by traditional methods, and should be multiplied by the DE. Under the assumption that m = 6 and ICC = 0.01, DE becomes 1.05. To compare 17.8% vs 2.7% surgical complication rates for a (*not clustered*) randomized trial, with 84% power, and 0.05 type I error rate, we would need to enroll 136 patients total. This is also listed in the sample size calculator above under the "unadjusted box". For a DE value of 1.05, this sample size should be multiplied by 1.05 to find the sample size of a cluster randomized trial to reach same power. Therefore, the sample size of the clustered randomized trial would be 136 x 1.05 = 142.8 ~143.

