#### Aim 1: Power Calculations

For the purpose of sample size estimation, data from in the Park-Reeves Syringomyelia Research Consortium (PRSRC) were analyzed (ambispective enrollment, n=589 subjects with complete data); specifically, surgical complications  $\leq 12$  months were used to calculate the sample size. In

this dataset, surgical complications were noted in 17.8% of PFDD cases and 2.7% of PFD cases. This is consistent with reported values from a recent meta-analysis, where the rates for CSF-related complications for PFDD and PFD were 18.5% and 1.8%, respectively [27], as well data reported in case series [17, 25] and a systematic review [42]. We expect to observe a similar difference in PFDD versus PFD cases in the proposed study. Because of the clustered randomized nature of the trial, the intraclass correlation coefficient (ICC) should be taken into account. The ICC is defined as the proportion of the between cluster (PRSRC center) variation to the total variation. Since the cluster sizes are small (6 per center), and we have a large number of centers available for enrollment (48 total), the effect of ICC on sample size will be small. Thus, using the PRSRC values of 17.8% for PFDD and 2.7% for PFD, and assuming equal number of subjects per group and twosided type I error rate of 0.05, to reach 90% power, 36 centers averaging 6 subjects per center will be required for the trial assuming the ICC is 0.05. To account for 2% dropout rate, we will recruit 48 centers with a cluster size averaging 6 subjects. Therefore, overall sample size of enrolled patients will be 148 patients, approximately 74 patients per procedure over the enrollment period. These numbers are achievable, as our data suggest there is >500 potential study candidates across the 48-center network over two years.

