The primary outcome is a binomial outcome measured as a surgical complication and/or requirement for reoperation for complication management ≤ 12 (+/- 2 months) months after initial PFDD or PFD. To account for within cluster correlation, possibly variable cluster size and the relatively small number of clusters in this cluster randomized trial, generalized estimating equations (GEE) with small-sample correction or random effect logistic regression will be used for the primary analysis of this cluster randomized trial [35, 36].

Specifically, a GEE model with a logit link function and adjustment for baseline covariates can be expressed as follows:

$logit(\pi_{ij}) = \mu + \delta T_i + x_{ij}\beta$

where $T_i = I$ if group *i* is assigned PFD and 0 otherwise. Accordingly, δ is the intervention effect. Let x_{ij} is the p-dimensional vector of group-level of individual level covariates from individual *j* (*j* = 1, ..., n_i) nested in center *i* (*i* = 1, ..., # of active centers here); and β is the vector of covariate effects. Also let the outcomes (CSF-related complication ≤ 6 months, yes/no) are independently distributed as $y_{ij} \sim \text{Bernoulli}(\pi_{ij})$. Further let, μ be the log-odds of positive outcome ($y_{ij} = 1$) for PFDD subjects with reference values for covariates ($x_{ij} = 0$) and average random effect ($\gamma_i = 0$). The exchangeable correlation structure will be used for the within-group homogeneity for the correlation structure of the outcomes. Note that, this correlation parameter corresponds to the intraclass correlation coefficient (ICC).

Specific Aim 2:

Hypothesis: Clinical improvement and syrinx regression provided by PFD will be non-inferior compared to those provided by PFDD.

Anticipated Outcome: Clinical symptoms, neurological function, and syrinx regression ≤ 12 months (± 2 months) provided by PFD will be non-inferior compared to those provided by PFDD. The non-inferiority margin is defined as the difference between the outcome rates by treatment. For the clinical improvement outcome, a non-inferiority margin of 0.17 units will be used. A non-inferiority margin of 0.135 units will be used for the syrinx regression outcome.

Clinical symptoms, neurological function, and syrinx regression are defined as rates of change from baseline to 12 months. The 1-sided confidence interval for the difference in rates between the PFD and PFDD groups will be calculated and compared to the corresponding non-inferiority margins.

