Second Chiari surgeries will be analyzed as 1) the proportion requiring a surgical revision and 2) the type of second surgery performed (same or cross-over). The 1-sided confidence interval for the difference in rates between the PFD and PFDD groups will be calculated and compared to the corresponding non-inferiority margins.

Specific Aim 3:

Hypothesis: With fewer surgical complications, PFD will be associated with superior QOL compared with PFDD.

Anticipated Outcome: PFD will have superior QOL and will show improvements in overall QOL over time (≤ 12 months post-operatively (± 2 months)) compared to PFDD. In particular, both physical metrics (evaluated by pain frequency, pain severity and non-pain symptoms) and psychosocial metrics will improve at a higher rate and in a shorter period of time after PFD compared to PFDD.

Secondary outcomes include Treatment Efficacy variables and Quality of Life variables. Continuous variables measured at 3 time points over the 12-month follow-up will be analyzed using longitudinal analysis with linear mixed models including the random cluster effect. Binomial and ordinal data will be analyzed using Mixed Model methods accounting for cluster. In addition, sensitivity analyses will be conducted where the missing data points will be imputed based on the last observation carried forward.

It should be noted that for Aim 3, primary analyses will be based on the QoL exam performed at 10 to 14-month window. A sensitivity analyses will also be performed based on the last QoL exam available at any time \geq 3 months after surgery. Analyses based on the mixed effect model will also be performed where both cluster effect and error terms will be random.

Missing data: Based on PRSRC data and early data from this trial, loss to follow-up rate is expected to be low (<2%). To prevent missing data, we will meet with patients at 1 month, 3-6 months and at 12+/-2 months after the procedure. Every effort, including phone call reminders to patients, will be made to decrease loss to follow-up. Loss to follow-up, missing data, and the reasons leading to loss of follow-up or data will be recorded. In case of missing data, we will impute missing data using different methods. Because of the repeated measures nature of the data, the 'last observation

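### Binary and ordinal secondary outcomes: the Protocol and SAP name different cluster models, and neither states a small-sample method for them

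*Protocol*

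**What the plan says.** Protocol section 9.5, Comparison methods, gives its reason for care as "possibly variable cluster size and the relatively small number of clusters in this cluster randomized trial". It then specifies that "generalized estimating equations (GEE) with small-sample correction or random effect logistic regression will be used for the primary analysis". The next paragraph turns to the secondary outcomes. Continuous variables get linear mixed models with a random centre effect. For the rest, "Binomial and ordinal data will be analyzed using GEE methods accounting for cluster". No correction is named there, and none is excluded.

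SAP section 7.5 keeps the primary wording. In the text under Specific Aim 3 that covers both the efficacy and the quality-of-life outcomes, it says: "Binomial and ordinal data will be analyzed using Mixed Model methods accounting for cluster". No degrees-of-freedom method is given.

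For Aim 2, SAP section 7.5 adds a separate procedure: "The 1-sided confidence interval for the difference in rates between the PFD and PFDD groups will be calculated and compared" with the non-inferiority margins, 0.17 for clinical improvement and 0.135 for syrinx regression. No variance method or adjustment for centre is stated for that interval. SAP section 1.2 makes clinical symptoms and syrinx regression the primary variables for Aim 2.

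**The concern.** The Protocol's reason for a small-sample correction applies equally to every outcome measured in the same centres. With few, unequal clusters the ordinary GEE sandwich standard error is too small on average and is itself imprecise, so a z test rejects too often and confidence intervals are too narrow. An analyst who finds the correction in one paragraph and not in the next could reasonably use the software default.

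These outcomes matter. Protocol section 2.2 says that PFD may give poorer symptom resolution and more revision surgery. Intervals that are too narrow could produce a false difference on such outcomes or, where a bound is compared with a margin, a false claim of non-inferiority. With two current documents naming different models, the choice of model and of error control is also left open until the data are in hand.

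**Working it through.** **1. Inputs**
- Centres: 24 of mean size 6, or 30 of mean size 5 (Protocol, Aim 1: Sample Size Recalculation). Elsewhere the documents give 36 + 7 = 43 (SAP section 2), 36 + 8 = 44 (Protocol, Design and Outcomes) and 48 (Protocol 4.3).
- cv of centre size: 1.08, given with a mean size of 2.9 in 47 patients, so about 47/2.9 = 16 centres (same Protocol subsection).
- ICC: 0.01 (recalculation) and 0.05 (original assumption).
- Rates in the PFDD arm: clinical improvement 78.6%, syrinx regression 89.1% (Protocol, Aim 2).
- Patients: 148.
- My assumptions: a low null rate of 10%, and cv values of 0 and 0.6 as alternatives.

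**2. The plan's own figures.** The documents state no error rate for the secondary tests, so the only figures to reproduce are those of the primary design. For 17.8% vs 2.7%, two-sided 0.05 and 84% power, n per arm = [1.960·√(2·0.1025·0.8975) + 0.994·√(0.178·0.822 + 0.027·0.973)]²/0.151² = 68.9. That is 69 per arm, or 138 in total. The unpooled form gives 66.1, so 134 in total. The plan states 136. With 145 patients and a design effect of 1.05, the effective n per arm is 145/2/1.05 = 69.05 and power is 84.05%, against 84% stated. The design inputs are therefore read correctly.

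**3. Why unequal size matters.** Take one arm with k centres, independence working correlation and ICC near 0. The sandwich variance is then biased by the factor 1 − Σ(nᵢ/N)², where Σ(nᵢ/N)² = (1 + cv²)/k.
- 24 centres (k = 12), cv 1.08: (1 + 1.1664)/12 = 0.181. Variance factor 0.819, SE factor √0.819 = 0.905. A z test then rejects 2Φ(−1.960·0.905) = 7.6%.
- 24 equal centres: 1/12 = 0.083. SE factor 0.957, rejection 6.1%.
- 43 centres (k = 21.5), cv 1.08: 0.101. SE factor 0.948, rejection 6.3%.

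This is bias alone. The imprecision of the variance estimate raises the rates further.

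**4. Simulation.** 4,000 trials per cell, 148 patients, centres split between arms, beta-binomial outcomes, logit link, no treatment difference. The routine's estimates and standard errors matched a standard GEE package on a test dataset. The table shows rejection at nominal two-sided 5%, null rate 78.6%, independence working correlation, as uncorrected z / Mancl-DeRouen with t on centres − 2.

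| Centres | cv | ICC 0.01 | ICC 0.05 |
|---|---|---|---|
| 24 | 1.08 | 9.1% / 3.9% | 10.2% / 4.4% |
| 30 | 1.08 | 8.4% / 4.0% | 9.3% / 4.6% |
| 36 | 1.08 | 7.6% / 3.6% | 9.1% / 4.6% |
| 43 | 1.08 | 6.8% / 3.9% | 7.4% / 4.5% |
| 24 | 0.6 | 7.4% / 3.6% | 8.9% / 3.9% |
| 30 | 0.6 | 7.2% / 3.7% | 7.5% / 4.3% |
| 24 | 0 | 7.4% / 3.9% | 6.4% / 3.0% |
| 30 | 0 | 6.2% / 3.6% | 6.0% / 3.7% |

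Monte Carlo standard error at 9% is √(0.09·0.91/4000) = 0.45 percentage points.
- Adding the 10% null rate and an exchangeable correlation held at or above zero, the uncorrected range for 24-30 centres and cv 1.08 is 7.6-10.2%.
- If the exchangeable correlation may go negative, that range becomes 10.4-15.5%. Exchangeable is the structure the SAP names for the primary model.
- Kauermann-Carroll standard errors with t on centres − 2 gave 5.2-6.6% (separate run of 6,000 trials per cell, 24-30 centres, cv 1.08).
- Further runs with cv 0.7, or with 42 centres, gave about 7-8% uncorrected.
- A random-centre mixed model, as in the SAP, rejected about 3-7% of the time.

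**5. Aim 2 interval.** True deficit set at the margin (0.17 or 0.135), nominal one-sided 5%, rate-difference scale, cv 1.08. With 24 centres, false passes were 7.3-8.9% with an uncorrected sandwich and 4.0-4.9% with Mancl-DeRouen and t. With 36-43 centres they were 6.2-8.0% and 4.2-6.0%.

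**The case against.** A reader might infer that the Protocol requires uncorrected GEE and that the trial's secondary tests will therefore run at 8-10%. The documents do not support that, for four reasons.

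First, the Protocol is silent on correction for the secondary GEE. The sentence comes one paragraph after a correction is named for the same centres, and it neither requires nor forbids one. For the primary analysis, the correction belongs to one of two permitted methods.

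Second, the later SAP (July 2021, based on Protocol Version 6) names mixed models, for which the error rate is close to nominal.

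Third, 24 and 30 centres are illustrative power scenarios, and the cv of 1.08 is an early snapshot from about 16 centres. With more centres or more even sizes, the excess shrinks.

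Fourth, in the SAP the Aim 2 non-inferiority claims go through a rate-difference interval, not through the quoted GEE sentence. The symptom score that SAP section 1.2 calls binary is averaged over visits and symptoms, so it may not be binomial at all. How many outcomes the GEE sentence governs is unclear.

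It is also tempting to stress that GEE and mixed models estimate different odds ratios (marginal and centre-conditional). At a 78.6% rate the log odds ratios differ by only about 1% at ICC 0.01 and 5% at ICC 0.05, so this is a minor matter.

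All four points stand, and they limit the size of the problem. They do not resolve the conflict between the documents, supply a small-sample method in either of them, or give the Aim 2 interval a variance.

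**Conclusion.** The concern holds as an inconsistency and an omission, with a conditional effect on error rates. The Protocol and SAP prescribe different models for the same secondary outcomes, and neither says how the small number of centres will be handled. If the Protocol's wording is followed with the ordinary sandwich standard error, the type I error at nominal 5% is about 8-10% with 24-30 centres and cv 1.08, about 7-8% with cv 0.7 or about 42 centres, and about 5-7% with 24-30 equal-sized centres. It is higher if an exchangeable correlation may go negative. If the SAP's mixed model is followed, it is about 3-7%.

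These figures rest on the centre counts, cv and ICCs quoted in the plan, on beta-binomial outcomes and on 148 patients. The final number of enrolling centres and the final cv are not given. The primary analysis is not affected.

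**What to change.** Name one model for binary and ordinal secondary outcomes in both Protocol section 9.5 and SAP section 7.5, with its small-sample method. Either of these would do:
- GEE with Mancl-DeRouen or Kauermann-Carroll standard errors and t on centres minus 2 degrees of freedom, with the working correlation stated and, if exchangeable, whether it is held at or above zero.
- The SAP's random-centre mixed model, with t on centres minus 2 degrees of freedom.

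In SAP section 7.5, Specific Aim 2, state that the one-sided interval for the difference in rates uses the same centre-adjusted, small-sample-corrected variance on the rate-difference scale (for example, an identity-link GEE). List which outcomes go through which analysis, including the averaged symptom score.

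The cost is a sentence or two in each document and no new data. Secondary intervals become about 10-25% wider than with uncorrected GEE. As an illustration, in one simulated dataset with 24 centres the standard error rose from 0.805 to 0.913, a factor of 1.134. With t on 22 degrees of freedom (2.074 against 1.960, a factor of 1.058), the interval is 1.134 × 1.058 = 1.20 times as wide. Some power for the secondary comparisons is lost in return for error rates near the nominal level.
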